1.0 INTRODUCTION

1.1 Pancreatic Cancer

Pancreatic cancer is the 10th most common cause of cancer, and the 4th most common cause of cancer-related death in the United States, with an annual incidence of 45,220 new diagnoses per year [1]. The only curative treatment for pancreatic cancer is surgery, yet approximately 75% of patients present with unresectable or metastatic disease. Of those patients with surgically resectable disease, the 5-year survival is around 20%. Among those with unresectable disease distant metastatic spread remains the primary problem, though up to 1/3 of patients will die from local tumor progression [2]. Additionally, local tumor progression leads to pain, gastrointestinal obstruction, or bleeding, all of which substantially decrease a patient's quality of life. Thus, local tumor control remains a crucial part of treatment for patients with pancreatic cancer who are not candidates for curative therapy.

1.2 Treatment options for locally advanced unresectable pancreatic cancer

The optimal treatment for locally advanced pancreatic cancer remains unclear, though current treatment often includes chemotherapy, or chemotherapy with radiotherapy. Unfortunately, patients with unresectable disease are not curable, and therefore chemotherapy is delivered with the intent of delaying disease progression, and lengthening life. Radiotherapy focuses on controlling the primary pancreatic tumor. Unfortunately, neither chemotherapy nor radiation has proven effective with unresectable pancreatic cancer, and the median overall survival for this disease is only around 10-12 months.

1.3 Radiation for locally advanced pancreatic cancer

Conventional radiotherapy in pancreatic cancer is given daily over 5-6 weeks with concurrent chemotherapy. The Gastrointestinal Tumor Study Group conducted a series of studies with chemoradiotherapy in pancreatic cancer defining its effectiveness. More recent series on chemoradiotherapy have yielded mixed results, with some reports of improved efficacy, and others without. A primary limitation of chemoradiation relates to the side effects including nausea, vomiting, and fatigue, with a substantial fraction of patients experiencing grade 3-4 toxicity. Unfortunately, despite its efforts, conventional chemoradiation has low local control rates often in the range of 50% or lower. Additionally, this 5-6 week treatment duration occupies a significant time burden for patients and caregivers, plus this can delay much needed systemic chemotherapy. In an attempt to improve local control and reduce treatment time investigators have started to use shorter more intense courses of radiotherapy, specifically, stereotactic body radiotherapy (SBRT).

1.4 Stereotactic body radiotherapy (SBRT) in pancreatic cancer

SBRT in pancreatic cancer shows great promise with initial studies showing high rates of local control. The initial study from Stanford escalated the dose of single fraction radiotherapy from 15 Gy in a single fraction to 25 Gy in a single fraction [3]. A subsequent phase II study treated patients to 45 Gy in 25 fractions with conventionally fractionated radiation, followed by 25 Gy in a single fraction [4]. Two of the 16 patients in this trial (13%) had grade 3 toxicity. Additional data with 25 Gy in a single fraction found

high rates of local tumor control with a 1-year freedom from local progression rate of 84% [5]. Unfortunately, the Stanford group found increased risk of late toxicity with the 25 Gy in 1 fraction regimen [6]. The close proximity of the stomach and duodenum put these organs at risk in radiotherapy directed at the pancreas. Of 73 patients treated with 25 Gy in a single fraction, 12 had grade 2-4 duodenal toxicity [6].

More recently, Stanford has preliminarily reported on a phase II trial 5-day course of SBRT [7]. This 5 fraction schedule going to 33 Gy was safe, with one reported toxicity event, though the efficacy was lower with decreased rates of local control. The observation that 33 Gy in 5 fractions was safe but had lower local control suggests that there may be room for dose escalation. This current trial will determine the maximal tolerated dose of SBRT in 5 fractions, for which the efficacy will be tested in a subsequent phase II trial.

This trial will escalate the dose from 40 Gy in 5 fractions, to 60 Gy in 5 fractions, at 5 Gy intervals. Comparing different radiation fractionation schedules is complex, though the standard metric used is the biologic effective doses (BED), and the BED of multiple radiation fractionation schedules is provided below in Table 1. The selection of a dose range with this study was based on a number of factors. First, the starting dose level of 45 Gy has been found safe in recently reported hypofractionated regimens in pancreatic cancer [8], in five fractions is the natural extension beyond 33 Gy in five fractions found safe by the Stanford researchers. The final dose level of 60 Gy in five translates into a BED of 132 for tumor response, and 300 for late toxicity. This final dose level is similar to that used by Koong, et al. with 141 for tumor response, and 305 for late toxicity.

Table 1. Biologic effective dose of different radiation regimens in pancreatic cancer

Radiation scheme	Protocol	Biologic effective dose	
		Tumor response ($\alpha/\beta = 10$)	Late toxicity ($\alpha/\beta = 3$)
Conventional radiation			
50 Gy in 25 fractions		60	83
Completed SBRT protocols			
25 Gy in 1 fraction	Koong, et al [3]	88	233
33 Gy in 5 fractions	Herman, et al [7]	55	106
45 Gy in 25 fractions, then 25 Gy in 1 fraction	Koong, et al [4]	141	305
45 Gy in 6 fractions	Tozzi, et al [8]	79	158
Proposed SBRT protocol			
Cohort 1: 40 Gy in 5 fractions		72	147
Cohort 2: 45 Gy in 5 fractions (starting dose level)		86	180
Cohort 3: 50 Gy in 5 fractions		100	217
Cohort 4: 55 Gy in 5 fractions		116	257
Cohort 5: 60 Gy in 5 fractions		132	300

1.5 Primary study hypothesis

The purpose of this study is to determine the maximum tolerated dose of five fraction stereotactic radiotherapy (SBRT) in pancreatic cancer.

1.6 Imaging/treatment correlative study background

This trial is designed to find the maximum tolerated dose (MTD) under a fixed 5-fraction SBRT regimen. To do this, it is necessary to verify that the treatment accuracy remains consistent throughout, so as to not be a confounding factor in the outcome. Perhaps the biggest contributing uncertainties are the inter- and intra-fractional organ motion, principally driven by patients' respiration. Physiological changes may also impact organ motion during SBRT. To compensate for organ motion, generic margins are commonly applied to the CTV, such as ITV and PTV. In this trial, 2-3 mm PTV margin will be used and may be trimmed further depending on the location of the duodenum or stomach. For such a tight margin, along with highly hypofractionated dose, it becomes prudent to validate that the image guidance technologies used in this trial are adequate to meet the demanded accuracy. To do this, this trial will employ the following sequence of imaging: 1) kV/kV to bones, 2) CBCT to soft tissue and fiducial markers (4DCBCT if available), 3) fluoroscopy to fiducial markers during free-breathing, and 4) repeat CBCT to soft tissue and fiducial markers (4DCBCT if available) at the end of treatment. This sequence of imaging will help minimize the initial setup uncertainties due to inter-fractional motion (steps 1-3) as well as to monitor the intra-fractional motion (step 4). In addition to these primary objectives, the images will be further analyzed to determine 1) the minimum adequate margin in each principal direction per patient population, 2) identify anatomical motion surrogates for when fiducials are not available, and 3) potential for various adaptive RT strategies.

2.0 OBJECTIVES

2.1 Primary Aim

2.1.1 To determine the maximum tolerated dose (MTD) of stereotactic body radiotherapy (SBRT) in pancreatic cancer.

2.2 Secondary Aims

- 2.2.1 To estimate the rate of local tumor progression after SBRT.
- 2.2.2 To estimate the rate of distant disease progression after SBRT.
- 2.2.3 To measure overall survival after SBRT.
- 2.2.4 To estimate a dose-response between radiation dose and local control.
- 2.2.5 To measure longitudinal quality of life before and after SBRT.

- 2.2.6 To determine the correlation between quality of life, and disease progression after SBRT.
- 2.2.7 To determine if any dose-volume parameters predict grade ≥ 3 duodenal toxicity.
- 2.2.8 To determine if patients are able to receive additional chemotherapy after SBRT.
- 2.2.9 To identify natural anatomical surrogates that best correlate with the motion of the fiducial markers.
- 2.2.10 To determine if adaptive RT would be beneficial.

3.0 PATIENT SELECTION

The eligibility criteria listed below are interpreted literally and cannot be waived.

3.1 Inclusion Criteria

- 3.1.1 Diagnosis: Histologically-proven invasive adenocarcinoma of the pancreas.
- 3.1.2 Disease Status: Medically unresectable (stage I-II), or locally advanced (stage III). Patients with distant metastases (stage IV) must have stable disease or improved disease (partial response, or complete response) per Response Evaluation Criteria In Solid Tumors (RECIST) criteria as determined on serial imaging following a course of chemotherapy.
- 3.1.3 Tumor Location: Primary tumor may be located anywhere in the pancreas.
- 3.1.4 Treatment eligibility: The patient must be able to have fiducial markers implanted into the pancreatic tumor, and receive radiation regimen as specified in the protocol.
- 3.1.5 Performance Level: Karnofsky Performance Status ≥ 60 (see Appendix II)
- 3.1.6 Adequate Renal Function Defined As:
 - Serum creatinine $\leq 1.5 \times$ upper limit of normal
- 3.1.7 Age: Patients must be 18 years of age or older.
- 3.1.8 Informed Consent: All subjects must sign a written informed consent.

3.2 Exclusion Criteria

- 3.2.1 Pregnancy or Breast-Feeding: Pregnant or breast-feeding women will not be entered on this study due to risks of fetal and teratogenic adverse events. (Note: Serum Pregnancy tests must be obtained in women of child bearing potential). Sexually active females may not participate unless they have agreed to use an effective contraceptive method (such as abstinence, diaphragm, condom, or intrauterine device) to prevent pregnancy for the duration of the study.

- 3.2.2 Life expectancy < 6 months
- 3.2.3 The patient cannot have had prior radiation therapy to the thorax or upper abdomen.
- 3.2.4 Incarcerated individuals
- 3.2.5 Subjects unable to give informed consent
- 3.2.6 Subjects with uncontrolled distantly metastatic disease per RECIST criteria (progressive disease) on imaging following chemotherapy

4.0 PRETREATMENT EVALUATIONS

The evaluations/interventions listed below should be done prior to the patient starting any protocol treatment (but may be done subsequent to the patient enrollment). In the unlikely event that results of any of these tests raise questions about the patient's eligibility for this study, please contact [name] immediately [contact].

- 4.1 Required Evaluations** (In addition to the mandatory pre-testing for eligibility in Section 3.0)
 - 4.1.1 History and physical examination including height, weight, and Karnofsky Performance Status (KPS).
 - 4.1.2 CT of the abdomen, and pelvis.
 - 4.1.3 Laboratory blood tests including CBC, comprehensive metabolic panel, and CA 19-9.

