10.0 PATIENT ASSESSMENTS

10.1 Study Parameters

Table 2

Study Procedures	Pre-Treatment	Week 1	Post-Treatment ^b
Informed Consent	X		
History and Physical	X		
Physical Exam with Vital Signs	X	X	1,3,6,9, 12 months, and every 6 months thereafter
CBC with differential, and comprehensive metabolic panel ^a	X		

CA 19-9	X		3, 6, 12, and every 6 months thereafter, or until disease progression
CT Abdomen, and Pelvis	X		3, 6, 12, and every 6 months thereafter, or until disease progression
Treatment: SBRT		D1-5	
Clinical evaluation for Toxicity	X	X	1,3,6,9, 12 months, and every 6 months thereafter
EORTC QLQ C-30/PAN26 questionnaire ^c	X		1,3,6,9, 12 months, and every 6 months thereafter

^a Electrolytes including Creatinine, Bilirubin, SGOT, and SGPT

^b Visit should occur at timepoints above +/- 28 days

^c See appendix for details on questionnaire

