12.1.2 Secondary Endpoints

12.1.2.1 Local control. The cumulative incidence of local failure will be determined for all patients treating distant progression or death as a competing

risk. Local progression will be defined as a $\geq 20\%$ increase in size on CT compared with CT prior to SBRT.

12.1.2.2 Distant metastatic progression rate. The cumulative incidence of distant metastatic failure will be determined for all patients treating death as a competing risk. In patients initially presenting with locally advanced disease, distant disease progression will be defined as the appearance of new metastatic lesions. In patients presenting with metastatic disease, distant progression will be defined as a $\geq 20\%$ increase in size on CT of the previously noted metastatic lesions.

12.1.2.3 Overall survival. Overall survival will be measured from the date of diagnosis through death of any cause. Survival will also be reported from the date of SBRT for comparisons to other trials in the literature. Finally, survival will be stratified by those with locally advanced disease, and those with metastatic disease on presentation.

12.1.2.4 Dose response. An exploratory analysis evaluating for a correlation between radiation dose response and local control will be done with a competing risk analysis, dividing patients into two groups stratified by the median dose..

12.1.2.5 Longitudinal quality of life. We will track longitudinal quality of life using the European Organization for Research and Treatment in Cancer (EORTC) quality of life core cancer questionnaire with the pancreatic cancer module (EORTC QLQ C-30/ PAN26) (see appendix). The questionnaire will be given prior to treatment, and periodically during follow-up visits after treatment has concluded. Trends will be assessed with a linear mixed effects model.

12.1.2.6 Correlation between quality of life and disease progression. Disease progression is a commonly used surrogate endpoint in clinical trial with pancreas cancer, however its relationship with quality of life has not clearly been demonstrated. Therefore, we will assess for correlation between quality of life and local or distant disease progression.

12.1.2.7 Dose-volume relationship with duodenal/gastric toxicity. We will plan to use logistic regression models to determine the relationship between grade ≥ 3 duodenal or gastric toxicity and dose to these structures. The dose to the duodenum will be extracted from our treatment planning system.

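### No chest imaging is scheduled in follow-up, so thoracic metastases have no protocol-defined measurement for a distant progression endpoint that has no anatomical limit

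*Combined protocol and SAP*

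**What the plan says.** All references are to the combined protocol and SAP.

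- **Baseline imaging.** Section 4.1.2 requires "CT of the abdomen, and pelvis". The list it belongs to is introduced as "In addition to the mandatory pre-testing for eligibility in Section 3.0", so it is not the whole baseline work-up.
- **Follow-up imaging.** The only diagnostic imaging row in Table 2 (section 10.1) is "CT Abdomen, and Pelvis", with post-treatment timing "3, 6, 12, and every 6 months thereafter, or until disease progression". There is no chest row.
- **Eligibility.** Section 3.1.2 says "Patients with distant metastases (stage IV) must have stable disease or improved disease" by RECIST, "as determined on serial imaging following a course of chemotherapy". It names neither the body region nor the modality, and it does not limit the metastatic site.
- **Endpoint.** Section 12.1.2.2 has two definitions. For patients who are locally advanced at entry, "distant disease progression will be defined as the appearance of new metastatic lesions". For patients who are metastatic at entry, it is a 20% or greater "increase in size on CT of the previously noted metastatic lesions". Neither definition is limited to an anatomical region. Death is the competing risk.
- **Other imaging.** The simulation CT (6.1.0.2) runs from T4/T5 to L5/S1. PET/CT may be fused for planning when available (6.1.1.2). Cone-beam CT is done on treatment days for positioning (6.1.2). None of these is scheduled again in follow-up.

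**The concern.** The endpoint covers metastases anywhere in the body, but the scheduled scans cover only the abdomen and pelvis. Two groups fall into the gap: stage IV patients whose known metastases lie in the thorax outside the abdominal field, and locally advanced patients whose new metastases appear there. For both, whether and when an event is recorded depends on a chest scan done for some other reason, and so on symptoms and local habit.

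At stake is aim 2.2.2, the rate of distant progression. Undetected events lower the cumulative incidence, and events found late shift the curve to the right. Two further analyses use the same event: local failure, which treats distant progression as a competing risk (12.1.2.1), and the correlation of quality of life with progression (12.1.2.6).

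**Working it through.** The plan gives no expected rate, sample size or precision for distant progression, so it has no figure to reproduce. The check is mainly a comparison of sections.

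**Step 1: can each definition be applied on the scheduled scans?**

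| Patient at entry | What 12.1.2.2 needs | What Table 2 supplies | Result |
|---|---|---|---|
| Stage IV, metastases in the abdomen or pelvis | Repeat CT of those lesions | Yes | Measurable |
| Stage IV, thoracic-only metastases outside the abdominal field | Repeat CT of those lesions | No | Growth rule cannot be applied on any scheduled scan |
| Locally advanced, new lesion in the abdomen or pelvis | Detection of the lesion | Yes | Detectable |
| Locally advanced, new lesion in the thorax | Detection of the lesion | No | Found only on an unscheduled scan or by chance at the edge of the field |

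**Step 2: does other protocol imaging close the gap?** No. The simulation CT shows part of the thorax, but only before treatment. PET/CT is optional and serves planning. Cone-beam CT ends with treatment. The eligibility imaging for stage IV ends at entry. If it does include the chest, a thoracic lesion is known at baseline and then has no scheduled repeat measurement.

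**Step 3: direction of the error.**

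- Distant failure: a patient who progresses in the chest undetected and then dies is counted under the competing event. One whose progression is found later is counted late. Both pull the curve down or to the right.
- Local failure: a patient whose distant progression is missed stays at risk, so a later local failure counts as a first event when the competing event should have come before it. The local failure curve moves up, if at all.
- Quality of life: a patient with undetected progression is classed as progression-free, which blurs the comparison.

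**Step 4: size.**

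Inputs: maximum sample size 30 (12.2.1). The thoracic-only share of distant events is not in the documents and is assumed to be 5% to 25%. True cumulative incidences of 60% and 40% are also assumed.

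Per missed patient: 1/30 = 0.033, or 3.3 percentage points of the crude proportion.

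Lowest observed incidence = true incidence × (1 − share). Most events missed = 30 × true incidence × share.

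| Assumed true incidence | Share 5% | Share 25% |
|---|---|---|
| 60% | 0.60 × 0.95 = 57%; 30 × 0.60 × 0.05 = 0.9 events | 0.60 × 0.75 = 45%; 30 × 0.60 × 0.25 = 4.5 events |
| 40% | 0.40 × 0.95 = 38%; 30 × 0.40 × 0.05 = 0.6 events | 0.40 × 0.75 = 30%; 30 × 0.40 × 0.25 = 3.0 events |

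The formula supposes that no thoracic event is ever found off schedule and that no such patient later has a countable abdominopelvic event. Relaxing either condition shrinks the loss, so for a given share the table shows the most that could be lost.

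**The case against.** The strongest reply is that the plan never confines the endpoint to Table 2 scans. Unscheduled chest imaging is not barred. The words on CT in 12.1.2.2 attach only to growth of known lesions; for new lesions no modality is named, so a lung metastasis found on any clinical scan meets the definition. A patient with chest and later liver progression would be recorded late, not lost. This stands, and it rules out the reading that thoracic metastases are never measured or that such a patient cannot become an event.

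A reader might also infer that no required scan at baseline shows the chest. The documents do not support that. The simulation CT covers T4/T5 downward, and a stage IV patient can enter only after serial RECIST imaging, which for thoracic-only disease would have to show those lesions. What remains at baseline is that no chest CT is specified.

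Nor does misplacement in the survival strata follow. Section 12.1.2.3 classifies patients by disease at presentation and does not tie that classification to the 4.1.2 CT.

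Finally, this is an estimation-only secondary aim with no test or decision rule. That limits the weight of the point, but it does not repair the mismatch: chance detection on unscheduled scans is unsystematic ascertainment, and its error runs in a known direction.

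**Conclusion.** The point holds in this form: no chest imaging is scheduled in follow-up and no baseline chest CT is specified, while eligibility and the endpoint admit metastases at any site. Ascertainment of thoracic progression is therefore unsystematic, and the cumulative incidence of distant failure is biased low or dated late. This part rests on the text alone.

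The size is uncertain. Each missed event costs 3.3 points in 30 patients. The range of 0.6 to 4.5 missed events rests on the assumed shares and incidences and is an upper bound on the loss under them, not a forecast. The effects on the local failure and quality-of-life analyses follow in direction but are not quantified here.

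The maximum tolerated dose, the toxicity scoring and the escalation and stopping rules do not use this endpoint and are unaffected. The correction is worth making because it changes what aim 2.2.2 can claim, and it is cheap.

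**What to change.** Preferred: change section 4.1.2 and the CT row of Table 2 to CT of the chest, abdomen and pelvis, at the same visits and in the same scanning session. The schedule then matches the endpoint as defined. The cost is a longer scan field, with a small added expense and radiation exposure.

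Alternative, with no added procedure: keep the present field and

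1. restate the 12.1.2.2 endpoint as abdominopelvic distant progression on scheduled CT;
2. leave patients whose only metastases are thoracic out of the growth-rule analysis;
3. report thoracic progression found on unscheduled imaging separately, labelled as incompletely ascertained, so that those events are not discarded.

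The cost is a narrower claim for aim 2.2.2. With this option, sections 12.1.2.1 and 12.1.2.6 should state which definition of distant progression they use.

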5.0 ENROLLMENT PROCEDURES

5.1 Recruitment

Subjects will be identified by study investigators and/or clinical research coordinators at participating centers. Information regarding the study will be included on the Moores UC San Diego Cancer Center Clinical Trials webpage and Clinicaltrials.gov.

5.2 Informed Consent

The investigational nature and objectives of the trial, the procedures and treatments involved and their attendant risks and discomforts, and potential alternative therapies will be carefully explained to the subject and a signed informed consent will be obtained.

